6.5.3 Subgroup analysis

Selected efficacy and safety analysis outlined in the [Section 6.5.1](#) and [Section 6.5.2](#) will be produced for patients treated with monotherapy pasireotide s.c., and those treated in combination with other therapies, separately. If there is a sufficiently large number of patients treated with a specific combination therapy, there might be a separate analysis for this subgroup of patients.

If the cohort of patients that have used pasireotide s.c. prior to study entry are heterogeneous or there are sufficient number of patients, selected safety and efficacy analysis will be done by subgroup of patients where the subgroup is based on duration of pasireotide s.c. use prior to study entry.

Furthermore, selected efficacy and safety analysis outlined in [Section 6.4.1](#), [Section 6.5.1](#) and [Section 6.5.2](#) will also be repeated for subgroup of patients coming from German Sites and other countries as requested.

Additional subgroup analysis may be defined in the report analysis plan (RAP).

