#### 8.2.1 Secondary efficacy endpoints

The secondary efficacy endpoints are as follows:

---

1. Proportion of patients with a mean UFC  $\leq$  ULN at 1, 3, 6, 12, 24 and 36 months after enrollment into the study.
2. The absolute and percentage change from baseline in biochemical measures of disease activity (mean UFC, serum cortisol, serum cortisol after dexamethasone, salivary cortisol, ACTH, fasting serum lipid profile (total cholesterol, HDL, LDL)) over time.
3. Proportion of patients achieving normalization of biochemical measures of disease activity (serum cortisol, serum cortisol after dexamethasone, salivary cortisol, ACTH) over time, where normalization refers to being within the upper and lower limit of normal ranges.
4. The absolute and percentage change from baseline in clinical signs and symptoms (blood pressure, body weight, body mass index, waist circumference) over time.
5. The proportion of patients with favorable shift from baseline in clinical symptoms of Cushing's disease over time.
6. The change from the last dose of pasireotide s.c. to 90 days after permanent discontinuation of pasireotide s.c. for patients who discontinue pasireotide s.c. prior to completing 3-year observation period. This change will be evaluated for all available continuous efficacy parameters.
7. The absolute and percentage change from baseline in tumor size over time.
8. The absolute and percentage change from baseline in patient reported outcome questionnaires (Cushing QoL and EURO QoL) over time.

All efficacy analyses will be done for all patients in the FAS and for the two cohorts. And all efficacy analyses except those under 5 will be done for the subgroup patients from German sites. Additionally, the efficacy analyses described under 1, 2, and 3 above will be repeated for the following subgroups of patients:

- Patients treated with monotherapy pasireotide s.c. throughout the study
- Patients treated with a combination of pasireotide s.c. with any other therapy for Cushing's disease throughout the study
- Patients who switched from monotherapy to combination therapy or vice versa at any time during the study

For all continuous efficacy variables (biochemical measures of disease activity, blood pressure, body weight, body mass index, waist circumference, tumor size), a Mixed Effects Repeated Measures Model will also be employed to assess the longitudinal changes in these variables.

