### **8.2.1.1 Proportion of patients with mean UFC $\leq$ ULN**

Analysis of all patients

In general, UFC is determined by collecting two or three 24-hour urine samples and calculating the mean of the 24-hour UFC values. However, routinely some sites may also use only one single 24-hour urine sample to assess UFC. Therefore in this study, mean UFC (mUFC) refers to the mean if more than one 24-hour UFC value was reported within 2 weeks and to the single value if only one value was reported.

If a 24-hour urine collection was performed but 24-hour UFC was not documented, 24-hour UFC will be calculated as product of 'urinary cortisol, random' (concentration of cortisol in 24-hour urine) and the total volume of 24-hour urine, if available.

For each time window (Month 1, 3, 6, 9, 12, 18, 24, 30 and 36), the number and proportion of patients with mean UFC (mUFC)  $\leq$  ULN will be presented together with corresponding exact (Clopper-Pearson) 95% confidence intervals (CI) for the proportions. The proportion will be calculated relative to the number of patients with a value for the respective time point (mUFC and ULN).

In addition, the number of patients without mUFC value and the number of patients with missing ULN (but mUFC value available) will be displayed by time window. In each time window, only those patients will be included who were treated during that window and followed up until the end of the respective time window.

Analysis of patients who discontinued pasireotide s.c.

A similar analysis will be performed for the subgroup of patients who discontinued pasireotide s.c. prematurely and had an assessment on-treatment and 90 days after last dose. The statistics described above will be displayed for the patient's last value on treatment and for the last value assessed during the 90 days after last dose. Furthermore, the status of the last mUFC value on treatment ( $\leq$  ULN,  $>$  ULN) will be cross-tabulated against the status 90 days after last dose.

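### SAP 8.2.1 forms the monotherapy and combination subgroups from treatment over the whole study, so results at early windows depend on later treatment

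*SAP*

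**What the plan says.** SAP 8.2.1 states that "the efficacy analyses described under 1, 2, and 3 above will be repeated for the following subgroups of patients". The first of the three groups is defined as "Patients treated with monotherapy pasireotide s.c. throughout the study". The second is its counterpart for pasireotide taken together with another Cushing's treatment, again over the whole study. The third takes everyone else and is worded as "Patients who switched from monotherapy to combination therapy or vice versa at any time during the study".

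Endpoint 1 is the proportion with mean urinary free cortisol (UFC) at or below the upper limit of normal, endpoint 2 the change from baseline in biochemical measures, and endpoint 3 the normalization of those measures.

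Under SAP 8.2.1.1 the endpoint 1 denominator is the patients who have a value at the time point, and in each window "only those patients will be included who were treated during that window and followed up until the end of the respective time window". No rule there counts the start of add-on therapy as non-response.

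Protocol 6.5.3 says that selected analyses "will be produced for patients treated with monotherapy pasireotide s.c., and those treated in combination with other therapies, separately". It does not require the regimen to hold for the whole study, and neither does the list of groupings in SAP 4.1.1.

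SAP 8.3 also classifies single, combination and switched therapy cumulatively from Day 1 to Day 30, 91, 183 and so on, but uses this only for the exposure summary.

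**The concern.** Membership is settled by everything that happens in up to three years of follow-up and is then applied to results at Month 1, 3 or 6. A patient who takes pasireotide alone for 20 months and then receives a second drug for Cushing's disease is absent from the monotherapy table at Months 1 to 18, although those values were obtained on monotherapy. They appear with the switchers instead.

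If the second drug was added because cortisol was not controlled, the patients removed are disproportionately non-responders, and the remaining group looks better than the group that started. A reader wanting a control rate on pasireotide alone will look at this table. The exact confidence interval printed beside the rate does not reflect the selection.

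**Working it through.** The documents give no response rate, switch rate or precision target for these subgroups, so there is no planned figure to reproduce. The check is selection arithmetic on assumed inputs.

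**Inputs, for one window, among patients who start on monotherapy**

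- r = true share controlled at that window (30% assumed).
- s0 = share of uncontrolled patients who receive add-on at any time (assumed).
- s1 = share of controlled patients who receive add-on at any time (assumed).

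**Formula.** Rate in the whole-study monotherapy group = r(1 − s1) / [r(1 − s1) + (1 − r)(1 − s0)]. Equivalently, the odds of control are multiplied by (1 − s1)/(1 − s0). The rate is therefore above r exactly when s0 > s1, equal to r when s0 = s1, and below r when s0 < s1.

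**Results for r = 30%**

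| s0 | s1 | Calculation | Rate shown |
|---|---|---|---|
| 20% | 0% | 0.30 / (0.30 + 0.56) | 34.9% |
| 30% | 0% | 0.30 / (0.30 + 0.49) | 38.0% |
| 50% | 0% | 0.30 / (0.30 + 0.35) | 46.2% |
| 30% | 10% | 0.27 / (0.27 + 0.49) | 35.5% |
| 30% | 30% | 0.21 / (0.21 + 0.49) | 30.0% |
| 10% | 20% | 0.24 / (0.24 + 0.63) | 27.6% |

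**Other starting rates.** The Protocol Introduction gives phase III responder rates at month 6 of 14.6% and 26.3%. They are illustrations only, because that definition also excluded patients whose dose was up-titrated. With s0 = 30% and s1 = 0 they become 0.146/(0.146 + 0.854 × 0.70) = 19.6% and 0.263/(0.263 + 0.737 × 0.70) = 33.8%.

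**In counts.** Suppose 100 patients start on monotherapy, 26 are controlled at an early window, and 22 of the 74 uncontrolled patients receive add-on later.

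- SAP rule: 26/(100 − 22) = 26/78 = 33.3% (exact 95% CI 23.1 to 44.9).
- Grouping by Day 1 regimen: 26/100 = 26.0% (exact 95% CI 17.7 to 35.7).

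The difference is about 7 percentage points and comes wholly from treatment given after the window.

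**Does anything else in the SAP correct this?** No. The sensitivity analyses in 8.2.1 deal with missing continuous values, not with group membership. The three tables cannot be recombined into the group that started on monotherapy, because the switched subgroup pools moves in both directions.

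**The case against.** The strongest reply has five parts.

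1. *Direction.* A reader might infer that the monotherapy rate is biased upward at every window. The documents do not support that. They report neither switch rates nor reasons for switching. A patient controlled at Month 3 who later loses control and receives add-on is removed as a Month 3 responder, which lowers the early rate. By Month 36, whole-study monotherapy and monotherapy so far nearly coincide. What then remains is whether add-on should count as failure. This part stands.

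2. *The switched group.* A reader might infer that it simply collects the failures. It also holds patients who moved from combination to monotherapy, possibly after gaining control. Some failures never reach it. Unsatisfactory therapeutic effect is a listed withdrawal reason (Protocol 3.4.1.1), and a patient on monotherapy until withdrawal stays in the monotherapy group. This stands.

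3. *Importance.* The wording about monotherapy or combination belongs to the primary safety objective (Protocol 2.1), not to the secondary efficacy objectives. The study is exploratory, with no hypothesis tests. "All efficacy analyses will be done for all patients in the FAS and for the two cohorts", and those results do not depend on this split. This stands and limits the point to descriptive subgroup tables.

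4. *Disclosure.* The subgroup label states its condition, switchers are shown, and SAP 8.3 counts them by period. This is true, but neither the label nor the counts turn the subgroup rate into one for patients who started on monotherapy.

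5. *Day 1 grouping has its own faults.* It would mix values after add-on into the monotherapy results for endpoint 2. In Cohort 2, Day 1 is the first dose during the study (SAP 6.1.5) and may follow more than 12 months of earlier use (SAP 4.2.1), so the regimen already reflects earlier response. Add-on would count as failure while discontinued patients still drop out of the denominator. These are fair and shape the fix, but they do not justify grouping on future treatment.

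**Conclusion.** The point holds in a limited form. As written, SAP 8.2.1 makes membership of the monotherapy and combination subgroups at early windows depend on treatment given later, and no other section corrects it.

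The monotherapy control rate is inflated if add-on is more frequent in uncontrolled than in controlled patients. That is plausible where treatment follows the investigator's judgment, but the documents do not establish it. On the assumptions above, a true 30% could appear as anything from 27.6% to 46.2%. With 30% of uncontrolled patients switching it is 38.0% if no controlled patient switches and 35.5% if 10% do.

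For the combination subgroup the direction cannot be determined, because patients may drop the second drug after gaining control or for other reasons. No error rate or power statement changes. It would be wrong to conclude that the study's overall efficacy results are distorted.

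**What to change.** Amend SAP 8.2.1 as follows.

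- **Endpoints 1 and 3:** group patients by regimen on Day 1 (single or combination) and keep them there. Count windows after the start of add-on as not controlled on monotherapy. Show the tables by cohort, because the Day 1 regimen means something different in Cohort 2. Footnote that discontinued patients still leave the denominator under SAP 8.2.1.1.
- **Endpoint 2:** classify therapy only from Day 1 up to each window, as SAP 8.3 does for exposure, so that values after add-on do not enter the monotherapy results. The SAP 8.3 periods end on target days, while a Month 3 value may be taken up to Day 136 (Table 6-2), so run the classification to the assessment date. At later windows this group is still selected, being patients not yet switched, but it uses no later information.
- **Existing three-group tables:** keep them as supportive, label them as conditional on post-baseline treatment, and split the switched group by direction.

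This is compatible with Protocol 6.5.3 and needs no new data, since dosing and concomitant therapy are already recorded. The cost is SAP wording, programming and a few more tables. The Day 1 rate also answers a slightly different question from the rate in patients who stayed on monotherapy, and the table titles should say so.

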6.5.1.5 Handling of missing data

For the analysis of these efficacy endpoints, for missing values, Mixed Effects Repeated Measured Model will be employed to assess the longitudinal changes in efficacy parameters. In addition, sensitivity analyses will be performed to assess the robustness of the efficacy findings.

The imputation method as well as sensitivity analyses will be specified in the RAP.

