### 6.1.7 Time windows

There is no visit schedule and no planned assessment in this non-interventional study. Assessment related data are collected as they become available during the study period. Therefore assessments are assigned to time windows based on the study day on which the assessment is performed. For mean UFC, the sample day of the first urine sample included in the calculation of mean UFC will be used for assignment to time windows.

If there are multiple values within a time window, the assessment closest to the target day of the time window will be used, if not indicated otherwise. If two assessments are equally close (e.g. 7 days before and 7 days after target day), the later will be used.

Time windows will be assigned according to the window schema in Table 6-2 if assessments are expected more frequently than every 6 months. Otherwise the time windows in Table 6-3 will be applied (e.g., for tumor volume, variables related to patient reported outcome questionnaires, findings of gallbladder ultrasound).

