### 6.2.3 Mixed model for repeated measures

The following SAS code will be used to fit the mixed model for repeated measures.

```
proc mixed;
  class patient window ;
  model outcome = window base /ddfm=kr;
  repeated window /patient = patient type=un;
  lsmeans window / cl;
run;
```

Here, `patient` denotes the patient identifier (e.g. SID1A), `window` the time window assigned, `outcome` the outcome variable (e.g. mean UFC), and `base` the corresponding baseline value.

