Except for the analysis of change from end of treatment to 90 days later, the efficacy analyses will only consider on-treatment values, defined as values assessed before end of treatment + 3 days.

All assessments will be assigned to time windows based on the study day on which the assessment was performed. If there are multiple values within a time window, the assessment closest to the target day of the time window will be used, if not indicated otherwise. Further details including the start and end days of the time windows are available in Appendix 16.1.9 of the CSR.

The continuous efficacy parameters will be also evaluated through a couple of sensitivity analyses: the first will be imputing the worst value at that time window in case of missing data and the second on the patients with the full set of values. The same Mixed Model will be employed for both the analyses.

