### **8.2.1.2 Absolute and percentage change from baseline in biochemical measures of disease activity**

For each time window (Month 1, 3, 6, 9, 12, 18, 24, 30, 36), observed values and, the absolute and percentage change from baseline in biochemical measures of disease activity (mean UFC, serum cortisol, serum cortisol after dexamethasone, salivary cortisol, ACTH, fasting serum lipid profile (total cholesterol, HDL, LDL) will be summarized with descriptive statistics. Distribution-free 95% CIs will be given for the median changes.

Furthermore, the time course of these parameters will be displayed graphically using box-plots.

In addition, the absolute and percentage change from the last assessment while on pasireotide s.c. to the last value during the 90-days follow-up period will be summarized in a similar manner.

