#### *8.2.1.6 Absolute and percentage change from baseline in tumor size*

For time windows Month 6, 12, 18, 24, 30, and 36, absolute and percentage change from baseline in tumor volume will be summarized with descriptive statistics. Distribution-free 95% CIs will be given for the median changes. This summary will only include post-baseline evaluations for which the same method of evaluation (CT scan or MRI) as at baseline.

In addition, the absolute and percentage change from the last assessment while on pasireotide

s.c. to the last value during the 90 days after drug discontinuation will be summarized in a similar manner.

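### Neither mixed-model sensitivity analysis in SAP 8.2.1 is a dependable robustness check as specified: one follows a single extreme value for skewed measures, and the other may keep few patients or none

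*SAP*

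**What the plan says.** Protocol 6.5.1.5 commits to a mixed model for the longitudinal efficacy data, says that "sensitivity analyses will be performed to assess the robustness of the efficacy findings", and leaves the details to the analysis plan.

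The SAP supplies them in section 8.2.1, for all continuous efficacy parameters. There are two analyses: "imputing the worst value at that time window in case of missing data and the second on the patients with the full set of values". It adds: "The same Mixed Model will be employed for both the analyses". The code in SAP 6.2.3 has "model outcome = window base /ddfm=kr" and "repeated window /patient = patient type=un", so the model is on the raw scale with an unstructured covariance. (The option after the slash should read subject=; that is a separate slip.) No simpler structure is named in case the fit fails.

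The number of windows depends on the parameter. SAP 8.2.1.2 gives nine for the biochemical measures, including ACTH and lipids: "For each time window (Month 1, 3, 6, 9, 12, 18, 24, 30, 36), observed values and". SAP 8.2.1.6 gives six for tumor size: "For time windows Month 6, 12, 18, 24, 30, and 36, absolute and percentage change from baseline in tumor volume". SAP 6.1.7 notes: "There is no visit schedule and no planned assessment in this non-interventional study". SAP 8.2.1 also limits efficacy analyses to values up to three days after the end of treatment, and asks for them by cohort as well as overall.

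**The concern.** A patient with no value in a window has no worst value of their own there, so the filled-in number must come from another patient. The natural reading is that every gap in a window receives the same number, the most extreme one observed, and that it is then treated as data. Worst is not defined, although SAP 8.2.1 treats both high and low cortisol and ACTH as abnormal. The SAP does not say whether windows after discontinuation are filled, or whether the window after Month 36 belongs to the full set.

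The full-set analysis has the opposite problem. In a study that collects assessments only as they occur, a patient with every window filled is unusual, and must also have stayed on drug for about three years.

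At stake is whether these runs can tell a reader how far the efficacy trends depend on missing data. A large shift in the first may reflect one outlier. Agreement in the second may reflect selection.

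**Working it through.** The plan has no figure to reproduce: the sample size of 100 to 200 is declared non-statistical, and no missing-data rate, SD or retention is given. Those are assumptions below, shown as ranges.

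**1. Worst-value filling.** After filling, every patient with a baseline value has every window, so the least-squares mean for a window is the plain mean of the filled data:

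filled mean = (1 − f) × observed mean + f × observed maximum, with f the share missing.

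For a log-normal measure with median 1 and log-SD s, the mean is exp(s²/2). The median of the maximum of n = (1 − f)N values is exp(s × z), where z is the normal quantile at 0.5^(1/n).

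With N = 100, f = 30%, s = 0.8:
- mean = exp(0.32) = 1.377
- n = 70, z = 2.332, maximum = exp(1.866) = 6.46
- filled mean = 0.7 × 1.377 + 0.3 × 6.46 = 2.90
- ratio to the observed mean = 2.90 / 1.377 = 2.11

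Simulation (4,000 runs) agrees: 2.10, with a 5th to 95th percentile range of 1.63 to 3.21. The R² between the filled mean and the single maximum is 0.99, and removing that patient moves the result by 27% of the observed mean. One patient's value occupies (30 + 1)/100 = 31% of the rows.

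The same formula gives these ratios of filled to observed mean:

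| Measure (assumed) | N | f = 10% | f = 30% | f = 50% |
|---|---|---|---|---|
| Log-normal, log-SD 0.5 | 100 | 1.20 | 1.55 | 1.83 |
| Log-normal, log-SD 0.8 | 100 | 1.40 | 2.11 | 2.62 |
| Log-normal, log-SD 0.8 | 200 | 1.51 | 2.42 | 3.10 |
| Log-normal, log-SD 1.2 | 100 | 1.79 | 3.10 | 3.93 |
| Normal, mean 130, SD 15 | 100 | 1.03 | 1.08 | 1.13 |

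More patients make it worse, because the maximum grows with n. In the blood-pressure-like row the shift at 30% is 0.3 × 2.332 = 0.70 SD, a real bias. But removing the largest value moves the result by only about 1%, and at 10% missing the R² with the maximum is 0.37.

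**2. Full set: number of patients.** An unstructured matrix has 9 × 10/2 = 45 parameters for nine windows and 6 × 7/2 = 21 for six. Once the window means are fitted, n complete patients give a residual matrix of rank at most n − 1, so nine windows need about 10 patients (checked: rank 8 at n = 9, rank 9 at n = 10).

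Expected complete patients = N × r × q⁹, where r is the share still on drug in the Month 36 window and q is the chance of a value in each window, taken as independent. With r = 50% (assumed):

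| N | q = 0.7 | q = 0.8 | q = 0.9 |
|---|---|---|---|
| 50 (a cohort) | 1.0 | 3.4 | 9.7 |
| 100 | 2.0 | 6.7 | 19.4 |
| 200 | 4.0 | 13.4 | 38.7 |

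The binomial chance of nine or fewer is 0.87 at N = 100, q = 0.8, and 0.004 at q = 0.9. In a cohort of 50 it is 0.49 even at q = 0.9. At q = 0.8 and N = 100, varying r from 30% to 70% moves the expected count from 4.0 to 9.4.

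**3. Full set: the schedule itself.** This step assumes no completeness rate. It places the frequencies in Protocol Table 3-1 and section 3.5.3.1 in the SAP windows.

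| Parameter | Suggested frequency | Windows left empty |
|---|---|---|
| Tumor volume (Table 6-3, six windows) | every 12 months | Months 6, 18, 30 |
| ACTH, lipids (nine windows, SAP 8.2.1.2) | every 6 months | Months 1, 3, 9 |
| UFC, Table 3-1 | monthly to Month 3, then every 3 months | none |
| UFC, stated minimum after control, from Month 6 | every 6 months | Month 9 |

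A patient followed at exactly the first two frequencies never has a full set. In those empty windows, worst-value filling would supply most of the data.

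**4. Who remains.** The Month 36 window opens on Day 1006 and values count only up to three days after treatment ends. A full-set patient was therefore dosed until about Day 1003 or later.

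**The case against.** A reader might infer that both analyses must fail for every parameter. The documents do not support that.

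- For near-symmetric measures with few gaps, worst-value filling is biased but does not hang on one patient. If it agreed with the main analysis, that would be informative as an extreme bound.
- Comparing the number of patients with 45 parameters is misleading, because each complete patient contributes nine values. With three-monthly UFC or monthly vital signs and good retention, the full-set model can be fitted in the whole Full Analysis Set.
- Independence of windows is pessimistic. At overall fill rates of 70%, 80% and 90%, independence gives 4%, 13% and 39% of patients complete; a beta-binomial with within-patient correlation 0.3 (assumed) gives 26%, 42% and 65%. Part of that clustering is discontinuation, which step 2 counts separately through r.
- SAP 6.1.7 sends measures not expected more often than six-monthly to Table 6-3. Six-monthly ACTH and lipids would fill all six of those windows. But SAP 8.2.1.2 lists Months 1, 3 and 9 for them, so the two sections need reconciling. Tumor volume is unaffected.

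A reader might also infer that the SAP orders windows after discontinuation to be filled. It is silent on this, and its on-treatment restriction points the other way.

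Finally, the study tests no hypotheses, its primary endpoint is safety, and the mixed model supplements descriptive summaries with distribution-free intervals for medians. That limits the consequence. It does not make the two checks work.

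**Conclusion.** The point stands in a limited form and should be acted on. For skewed measures the worst-value result is likely to be set by one patient: about 2.1 times the observed mean at N = 100, 30% missing and log-SD 0.8, and 1.2 to 3.9 times over the N = 100 ranges shown. Those inputs are assumptions. For near-symmetric measures the result is biased, by about 0.7 SD at 30% missing, without being outlier-driven.

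The full-set analysis may have too few patients for an unstructured covariance, especially by cohort; that too rests on assumed retention and fill rates. For tumor volume, and for ACTH and lipids under SAP 8.2.1.2, the near-empty full set follows from the suggested schedule. That schedule is advisory, so extra assessments could add some patients. Even where the model fits, it describes only patients who stayed on drug, so it cannot probe missingness linked to poor response.

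**What to change.** 1. Replace worst-value filling by multiple imputation from the mixed model, on the log scale for skewed measures, and only for windows in which the patient was still on pasireotide. Worsen the imputed values by amounts fixed in advance, for example 10%, 25% and 50%, and report where the conclusion changes. Define the direction of worsening for each parameter. The worst-value run may stay as a labelled extreme bound, with worst defined.
2. Define the full set per parameter by the windows its suggested frequency can fill: for example Months 12, 24 and 36 for tumor volume (3 × 4/2 = 6 covariance parameters), and Months 6, 12, 24 and 36 for UFC, ACTH and lipids (4 × 5/2 = 10). Fit the model on those windows only, name a simpler covariance for use if the unstructured one does not converge, and state that the result describes patients who stayed on drug. For UFC, confirm Month 6 before lock: a patient moved to six-monthly sampling straight after Month 3 would miss it.
3. Reconcile SAP 6.1.7 with 8.2.1.2 on the windows for ACTH and lipids.

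The cost is SAP text and modest programming. The penalty sizes are a judgement, which is why they must be fixed before the data are seen. The reduced full set gives up the intermediate windows but keeps Month 36, which matters in a long-term study.
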